2.3. Study Design

This study will be a Phase 1, open-label, randomized, 2-way crossover, single dose study to estimate the relative bioavailability of PF-06291826 (tafamidis) variant 12.2 mg tafamidis free acid tablets and proposed commercial 12.2 mg tafamidis tablets administered under fasted conditions in healthy participants.

A total of 12 participants will be enrolled. Participants withdrawn from the study may be replaced. Each period will be separated by a washout of at least 16 days between administration of study drug. On Day 1 of each period, participants will receive a single dose of one of the two tafamidis formulations according to the study schema provided in Table 2:

Table 2. B3461102 Treatment Sequence Schema

Sequence	Period 1	Period 2
1 (n=6)	A	B
2 (n=6)	B	A

A: 1 x Variant 12.2 mg tafamidis free acid tablet (Test)

B: 1 x Proposed commercial 12.2 mg tafamidis free acid tablet (Reference)

3. ENDPOINTS AND BASELINE VARIABLES: DEFINITIONS AND CONVENTIONS

3.1. Primary Endpoints

The primary endpoints are plasma AUC_{inf} (if data permit, otherwise AUC_{last}) and C_{max} of tafamidis administered as variant 12.2 mg tafamidis free acid tablet (Test) and proposed commercial 12.2 mg tafamidis free acid tablet (Reference), under fasted conditions. Adjusted geometric mean ratios of AUC_{inf} , AUC_{last} and C_{max} will be derived to estimate relative bioavailability.

3.2. Secondary Endpoint

Not applicable.

CCI

Table 3. Plasma Tafamidis Pharmacokinetic Parameters Definitions

Parameter	Definition	Method of Determination
AUC_{last}	Area under the concentration-time curve from 0 to time of last measurable concentration	Linear/Log trapezoidal method
AUC_{inf}^*	Area under the concentration-time curve from time 0 to infinity	$AUC_{(0-tlast)} + (C_{last}^* / k_{el})$, where C_{last}^* is the estimated plasma concentration at the last quantifiable time point (C_{last}) estimated from the log-linear regression analysis $C_{last}^* = C_{last} \times e^{(-k_{el} \times t_{last})}$
CCI		
C_{max}	Maximum observed concentration	Observed directly from data
CCI		

*if data permit

CCI

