9.5. Sample Size Determination

A sample size of 12 participants will provide adequate precision to estimate the relative bioavailability of PF-06291826 (tafamidis) variant 12.2 mg tafamidis free acid tablets versus proposed commercial 12.2 mg tafamidis tablets administered under fasted conditions in healthy participants. The following table presents the width of 90% CI for different estimated effects, with 80% coverage probability.

Parameter	Estimated Effect (100*Test/Reference)	90% CI		CI Width
AUC	85%	78.15%	92.46%	14.31%
	90%	82.74%	97.89%	15.15%
	95%	87.34%	103.33%	15.99%
	100%	91.94%	108.77%	16.83%
	105%	96.53%	114.21%	17.68%
	110%	101.13%	119.65%	18.52%
	115%	105.73%	125.09%	19.36%
C _{max}	85%	76.75%	94.14%	17.38%
	90%	81.27%	99.67%	18.41%
	95%	85.78%	105.21%	19.43%
	100%	90.30%	110.75%	20.45%
	105%	94.81%	116.29%	21.48%

Parameter	Estimated Effect (100*Test/Reference)	90% CI		CI Width
	110%	99.32%	121.82%	22.50%
	115%	103.84%	127.36%	23.52%

These estimates are based on the assumption that within participant standard deviations of 0.098 and 0.119 for $\log_e AUC_{inf}$ and $\log_e C_{max}$, respectively, obtained as an average from studies B3461030, B3461044 and B3461095.

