3.4. Baseline Variables

Baseline characteristics will be collected according to the schedule of activities (SoA) as specified in the protocol.

CCI

PFIZER CONFIDENTIAL

CCI**4. ANALYSIS SETS (POPULATIONS FOR ANALYSIS)**

Data for all participants will be assessed to determine if participants meet the criteria for inclusion in each analysis population prior to releasing the database and classifications will be documented per standard operating procedures.

Participant Analysis Set	Description
Enrolled	“Enrolled” means a participant’s, or their legally authorized representative’s, agreement to participate in a clinical study following completion of the informed consent process and randomization/assignment to study intervention. A participant will be considered enrolled if the informed consent is not withdrawn prior to participating in any study activity after screening. Potential participants who are screened for the purpose of determining eligibility for the study, but do not participate in the study, are not considered enrolled, unless otherwise specified by the protocol.
Full analysis set	Example: All participants randomly assigned to study intervention and who take at least 1 dose of study intervention.
CCI	[REDACTED]
PK Concentration	The PK concentration population is defined as all participants who receive at least 1 dose of tafamidis and who have at least 1 measurable concentration of tafamidis.
PK Parameter	The PK parameter population is defined as all participants who receive at least 1 dose of tafamidis and who have at least 1 of the PK parameters of interest calculated.

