5.3. Methods to Manage Missing Data

5.3.1. Pharmacokinetic Data

Methods to handle missing PK data are described below.

Concentrations Below the Limit of Quantification:

In all data presentations (except listings), concentrations below the limit of quantification (BLQ) will be set to zero. (In listings BLQ values will be reported as “<LLQ”, where LLQ will be replaced with the value for the lower limit of quantification.).

Deviations, Missing Concentrations and Anomalous Values:

In summary tables and plots of median profiles, statistics will be calculated having set concentrations to missing if 1 of the following cases is true:

1. A concentration has been collected as ND (ie, not done) or NS (ie, no sample).
2. A deviation in sampling time is of sufficient concern or a concentration has been flagged anomalous by the pharmacokineticist.

Note that summary statistics will not be presented at a particular time point if more than 50% of the data are missing.

An anomalous concentration value is one that, after verification of bioanalytical validity, is grossly inconsistent with other concentration data from the same individual or from other participants. For example, a BLQ concentration that is between quantifiable values from the same dose is considered as anomalous. Anomalous concentration values may be excluded from PK analysis at the discretion of the PK analyst.

PK Parameters:

Actual PK sampling times will be used in the derivation of PK parameters. If a PK parameter cannot be derived from a participant's concentration data, the parameter will be coded as NC

(ie, not calculated). (Note that NC values will not be generated beyond the day that a participant discontinues).

In summary tables, statistics will not be presented for a particular treatment group if more than 50% of the data are NC. For statistical analyses, PK parameters coded as NC will also be set to missing.

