If an individual participant has a known biased estimate of a PK parameter (due for example to dosing error or an unexpected event such as vomiting before all the compound is adequately absorbed from the gastrointestinal tract), this will be footnoted in summary tables and will not be included in the calculation of summary statistics or statistical analyses. For instance, if a participant has a vomiting event post dose that is within a duration of time that is 2-times the derived median T_{max} for the population for the administered treatment, then the pharmacokineticist should consider the exclusion of the PK concentration data collected following the initial vomiting event in that treatment period and the PK parameter data reported for that treatment period from the datasets used to calculate summary statistics or statistical analyses.

CCI

[figure not shown]
[figure not shown]

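### Does AUClast, the fallback primary AUC, need a common end time across the two periods?

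*SAP*

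**What the plan says.** SAP 3.1 sets the endpoint: "The primary endpoints are plasma AUC_{inf} (if data permit, otherwise AUC_{last}) and C_{max} of tafamidis". SAP Table 3 defines AUClast as "Area under the concentration-time curve from 0 to time of last measurable concentration", computed by the linear/log trapezoidal rule. SAP 6.1 models AUCinf, AUClast, AUC72 and Cmax separately on the log scale, with sequence, period and treatment fixed and participant within sequence random.

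Three rules decide whose values enter the model:

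- SAP Section 4 admits to the PK Parameter set participants "who have at least 1 of the PK parameters of interest calculated".
- SAP 5.3.1 deals with parameters that cannot be derived from a participant's "concentration data, the parameter will be coded as NC" and treats those as missing in the model.
- SAP 5.3.1 also covers a "known biased estimate of a PK parameter (due for example to dosing error or an unexpected event such as vomiting" before absorption is complete. Such a value is footnoted and left out of both the summary statistics and the statistical analyses.

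SAP 6.1 adds a residual check. If outliers appear, their effect on the conclusions is investigated, including by analyses without them.

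Protocol Table 2 schedules samples to 168 h in each period. Protocol 4.1 keeps participants in the unit for 8 days per period.

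**The concern.** A crossover compares each participant with themselves, so the two areas should cover the same span. AUClast does not guarantee this. A profile cut short still yields an AUClast, so the not-calculated rule does not catch it, and the analysis set asks for no minimum duration. The biased-estimate rule names dosing error and vomiting but not short sampling.

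If one full and one short area from the same participant both entered the model, two things would follow. The Test/Reference ratio would absorb the difference in sampling time, and the false within-participant difference would inflate the residual variance behind the 90% confidence interval. With 12 participants and precision as the only stated basis for the sample size, one such case could matter.

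**Working it through.** **Inputs from the documents.** SAP 2.3: "A total of 12 participants will be enrolled", six per sequence. Protocol 9.5: "within participant standard deviations of 0.098 and 0.119" for log AUCinf and log Cmax. No SD is given for AUClast, so 0.098 is applied to it as an assumption. Sampling times are those of Protocol Table 2.

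**Assumptions.** The visible text gives no half-life, so 30 to 77 h is used. The top value reads the 16-day washout as five half-lives: 16 × 24 / 5 = 76.8 h. Profiles are one-compartment with an absorption rate of 1/h.

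**The plan's own figure.** Protocol 9.5 states: "The following table presents the width of 90% CI for different estimated effects, with 80% coverage probability". The log half-width is t(0.95, 10 df) × SD × √(2/12) × √(χ²(0.80, 10 df)/10).

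- AUC: 1.8125 × 0.098 × 0.40825 × 1.1594 = 0.0841, which gives 91.94% to 108.77%, width 16.83. This matches the protocol table.
- Without the 80% factor, the half-width is 0.0725 and the width 14.52. That is the baseline below.

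**Effect of one short profile.** Let f be the area to truncation divided by the area to 168 h, and d = ln f. In a 6 + 6 crossover each participant's difference has weight 1/12.

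- Shift in the ratio: exp(d/12) − 1.
- Multiplier on the standard error: √[(10 × 2 × 0.098² + (5/6)d²) / (10 × 2 × 0.098²)].

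Example, 24 h stop with half-life 50 h: f = 0.302 and d = −1.196. The shift is exp(−0.0997) − 1 = −9.5%. The multiplier is √[(0.1921 + 1.1920)/0.1921] = 2.68. The interval width becomes 35.5 points.

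Test truncated, half-life 30/40/50/60/77 h:

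| Profile ends at | Shift in ratio (%) | SE multiplier |
|---|---|---|
| 24 h | −7.0/−8.4/−9.5/−10.3/−11.2 | 2.06/2.42/2.68/2.89/3.14 |
| 48 h | −3.2/−4.3/−5.1/−5.8/−6.6 | 1.29/1.49/1.66/1.79/1.97 |
| 72 h | −1.6/−2.4/−3.0/−3.5/−4.1 | 1.08/1.17/1.26/1.33/1.44 |
| 144 h (168 h missing) | −0.1/−0.3/−0.4/−0.5/−0.6 | 1.00 to 1.01 |

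A stop at 12 h gives −11.6 to −16.2%. If Reference is the short profile, the 24 h shift is +7.5 to +12.6%. A 10% fall needs f ≤ 0.28, meaning sampling that ends by about 14 to 28 h. Doubling the log-scale width needs f ≤ 0.44, meaning an end by about 24 to 46 h.

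**Would the plan catch it?** The SD of a within-participant difference is 0.098 × √2 = 0.139. For half-lives of 40 to 60 h, d at 24 h is −1.058 to −1.300, or 7.6 to 9.4 planning SDs. The profile also inflates the SD it is judged against. At 50 h the fitted residual is (5/6) × 1.196 = 0.997 against 0.139 × 2.68 = 0.372. Dividing 0.997/0.372 by √(5/6) gives a studentised value of about 2.9, where the most possible with 10 df is √10 = 3.16. It would stand out on the planned plots.

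**What exclusion costs.** With 11 complete pairs (5 + 6) the ratio is unbiased and the 80%-coverage width is about 18.0, against 16.83 with 12.

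**Would the fallback be invoked?** The area beyond 168 h is about 2^(−168/half-life): 5%, 10% and 14% at 40, 50 and 60 h. AUCinf should then usually be estimable and stay primary. A single profile cut at 24 h would make that one AUCinf hard to derive, but nothing in the plan says this switches the endpoint for the study.

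**The case for a change.** The strongest case for acting is that the plan foresees short profiles and leaves their handling open. Protocol Table 1 has an early-termination column with a PK sample, participants may withdraw at any time, and replacing a withdrawn participant does not remove the data already collected. The biased-estimate rule does not mention short sampling. The outlier step is only investigative, follows visual inspection, and takes place in an open-label study. A minimum end time fixed in advance would cost a sentence and would remove a judgement made with the results in view.

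The wording gap stands. The rest weakens on inspection:

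- **Rarity.** A participant who leaves in Period 1 and does not return adds essentially no within-participant contrast. Missing intermediate samples do not shorten a profile; every later sample must be lost. The damaging case is in practice an exit on about Day 2 of Period 2, during residence.
- **Coverage.** The examples in SAP 5.3.1 are introduced as examples. A 24 h area where 168 h was planned is plainly biased, and it can be identified from recorded sampling times without looking at the treatment comparison.
- **Cross-check.** AUC72 is modelled with the same code, so a distorted AUClast ratio would sit beside one over a common span.
- **Cost of the alternatives.** Making AUC72 the fallback discards data from 72 to 168 h for all 12 participants and changes an endpoint the protocol names. Cutting both of a participant's periods at the earlier end time gives a non-standard interval that varies between participants. A not-calculated rule would drop the same participant that the existing exclusion already drops.

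**Conclusion.** No change is needed. SAP Table 3 sets no common or minimum end time for AUClast, and a kept 24 h Test profile would move the ratio by about 7 to 11% and widen the log-scale interval 2.1 to 3.1 times. At 48 h or later the shift is under 7% and the widening less than twofold. These sizes rest on one affected participant of 12, an assumed half-life of 30 to 77 h, the AUCinf SD applied to AUClast, and the short profile being kept.

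That last condition is the one the plan already guards against. Large truncations fall under the exclusion in SAP 5.3.1 and would be plain in the residual check in SAP 6.1. Those that might pass unnoticed, such as a missing 168 h sample, shift the ratio by 0.6% at most. Exclusion widens the planned interval only from 16.83 to about 18.0 points. Followed sensibly, the plan gives a sound AUClast comparison in a study that tests no hypothesis. Naming short sampling as a further example would tidy the text but would not alter the analysis.

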3.4. Baseline Variables

Baseline characteristics will be collected according to the schedule of activities (SoA) as specified in the protocol.

CCI

PFIZER CONFIDENTIAL

CCI**4. ANALYSIS SETS (POPULATIONS FOR ANALYSIS)**

Data for all participants will be assessed to determine if participants meet the criteria for inclusion in each analysis population prior to releasing the database and classifications will be documented per standard operating procedures.

Participant Analysis Set	Description
Enrolled	“Enrolled” means a participant’s, or their legally authorized representative’s, agreement to participate in a clinical study following completion of the informed consent process and randomization/assignment to study intervention. A participant will be considered enrolled if the informed consent is not withdrawn prior to participating in any study activity after screening. Potential participants who are screened for the purpose of determining eligibility for the study, but do not participate in the study, are not considered enrolled, unless otherwise specified by the protocol.
Full analysis set	Example: All participants randomly assigned to study intervention and who take at least 1 dose of study intervention.
CCI	[REDACTED]
PK Concentration	The PK concentration population is defined as all participants who receive at least 1 dose of tafamidis and who have at least 1 measurable concentration of tafamidis.
PK Parameter	The PK parameter population is defined as all participants who receive at least 1 dose of tafamidis and who have at least 1 of the PK parameters of interest calculated.

5. GENERAL METHODOLOGY AND CONVENTIONS

Final analysis will be performed after study participant data set release following last participant last visit.

5.1. Hypotheses and Decision Rules

No statistical hypothesis will be tested in this study.

5.2. General Methods

5.2.1. Analyses for Binary/Categorical Endpoints

For binary or categorical variables, number of participants, numbers and percentages of participants meeting the categorical criteria will be presented in accordance with the Clinical Data Interchange Standards Consortium and Pfizer Standards (CaPS).

5.2.2. Analyses for Continuous Endpoints

For continuous variables, the data will be summarized using the number of participants, mean, median, standard deviation (SD), minimum, and maximum in accordance with the CaPS. For appropriate PK parameters, geometric mean and geometric coefficient of variation (%CV) will also be summarized.

5.3. Methods to Manage Missing Data

5.3.1. Pharmacokinetic Data

Methods to handle missing PK data are described below.

Concentrations Below the Limit of Quantification:

In all data presentations (except listings), concentrations below the limit of quantification (BLQ) will be set to zero. (In listings BLQ values will be reported as “<LLQ”, where LLQ will be replaced with the value for the lower limit of quantification.).

Deviations, Missing Concentrations and Anomalous Values:

In summary tables and plots of median profiles, statistics will be calculated having set concentrations to missing if 1 of the following cases is true:

1. A concentration has been collected as ND (ie, not done) or NS (ie, no sample).
2. A deviation in sampling time is of sufficient concern or a concentration has been flagged anomalous by the pharmacokineticist.

Note that summary statistics will not be presented at a particular time point if more than 50% of the data are missing.

An anomalous concentration value is one that, after verification of bioanalytical validity, is grossly inconsistent with other concentration data from the same individual or from other participants. For example, a BLQ concentration that is between quantifiable values from the same dose is considered as anomalous. Anomalous concentration values may be excluded from PK analysis at the discretion of the PK analyst.

PK Parameters:

Actual PK sampling times will be used in the derivation of PK parameters. If a PK parameter cannot be derived from a participant's concentration data, the parameter will be coded as NC

(ie, not calculated). (Note that NC values will not be generated beyond the day that a participant discontinues).

In summary tables, statistics will not be presented for a particular treatment group if more than 50% of the data are NC. For statistical analyses, PK parameters coded as NC will also be set to missing.

If an individual participant has a known biased estimate of a PK parameter (due for example to dosing error or an unexpected event such as vomiting before all the compound is adequately absorbed from the gastrointestinal tract), this will be footnoted in summary tables and will not be included in the calculation of summary statistics or statistical analyses. For instance, if a participant has a vomiting event post dose that is within a duration of time that is 2-times the derived median T_{max} for the population for the administered treatment, then the pharmacokineticist should consider the exclusion of the PK concentration data collected following the initial vomiting event in that treatment period and the PK parameter data reported for that treatment period from the datasets used to calculate summary statistics or statistical analyses.

CCI

[figure not shown]
[figure not shown]

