6. ANALYSES AND SUMMARIES

6.1. Primary Endpoints

For assessment of the relative bioavailability objective of the study, natural log transformed AUC_{inf} , AUC_{last} , AUC_{72} and C_{max} will be analyzed separately using a mixed effect model with sequence, period and treatment as fixed effects and participant within sequence as a random effect. Estimates of the adjusted mean differences (Test-Reference) and corresponding 90% confidence intervals will be obtained from the model. The adjusted mean differences and 90% confidence intervals for the differences will be exponentiated to provide estimates of the ratio of adjusted geometric means (Test/Reference) and 90% confidence intervals for the ratios. Treatment A (Variant 12.2 mg tafamidis free acid tablet) will be the Test treatment, while Treatment B (proposed commercial 12.2 mg tafamidis free acid tablet) will be the Reference treatment.

Residuals from the models will be examined for normality and the presence of outliers via visual inspection of plots of residuals vs predicted values and normal probability plots of residuals but these will not be included in the CSR. If there are major deviations from normality or outliers then the effect of these on the conclusions will be investigated through alternative transformations and/or analyses excluding outliers. Justification for any alternative to the planned analysis will be given in the report of the study.

CCI

PFIZER CONFIDENTIAL

Table 4. PK Parameters to be Summarized Descriptively by Treatment

Parameter	Summary Statistics
AUC_{inf} , AUC_{last} , [REDACTED] [REDACTED]	N, arithmetic mean, median, SD, %CV, minimum, maximum, geometric mean and geometric %CV
C_{max}	
F	

For AUC_{inf} , AUC_{last} , and C_{max} , individual participant parameters will be plotted against treatment. Box and whisker plots for AUC_{inf} (if data permits), AUC_{last} , [REDACTED], and C_{max} , will be plotted by treatment.

[REDACTED]
[REDACTED]
[REDACTED]

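### Does the discretion in SAP 5.3.1 to drop an anomalous concentration let a value slip past the outlier check in SAP 6.1?

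*SAP*

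**What the plan says.** SAP 5.3.1 (Pharmacokinetic Data) calls a concentration anomalous if, after the assay has been checked, it is "grossly inconsistent with other concentration data from the same individual or from other participants". It gives no numerical threshold. Its one example is that "a BLQ concentration that is between quantifiable values from the same dose is considered as anomalous". Such values are treated in two ways:

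- In summary tables and median plots, the value is set to missing where "a concentration has been flagged anomalous by the pharmacokineticist".
- For the PK analysis itself, "Anomalous concentration values may be excluded from PK analysis at the discretion of the PK analyst".

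The same section says that, outside listings, "concentrations below the limit of quantification (BLQ) will be set to zero".

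SAP Table 3 gives the method for Cmax as "Observed directly from data". AUClast and AUCinf are also derived from the concentrations, so an exclusion takes effect before any model is fitted.

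SAP 6.1 then looks at residuals from the mixed model. If there are outliers or marked non-normality, "the effect of these on the conclusions will be investigated through alternative transformations and/or analyses excluding outliers", and "Justification for any alternative to the planned analysis will be given in the report of the study". The residual plots themselves stay out of the study report.

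**The concern.** An aberrant peak concentration and an outlying Cmax can be the same number, and the SAP appears to give it two fates. If it reaches the model and stands out, its influence must be investigated and any departure from the planned analysis justified. If the PK analyst labels it anomalous one step earlier, it leaves no residual. Because removal under 5.3.1 is part of the plan, the justification sentence in 6.1 does not cover it either.

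The visible text requires neither a reason nor a decision date, and sponsor staff know the treatment (Protocol 6.4.3). The Test/Reference ratio and its 90% interval are the study's main output and inform dissolution specifications. With 12 participants, one value can move both.

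Three wording points add to the impression of looseness:

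- A flagged value is missing from the tables but only possibly excluded from the analysis.
- A BLQ value between quantifiable ones could be read as zero or as missing.
- The text on biased parameters is firm in one sentence and permissive in the next.

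**Working it through.** **Inputs.** Within-participant log SD for Cmax 0.119, and the 90% interval at 80% coverage probability (Protocol 9.5); 12 participants, 6 per sequence (SAP 2.3), hence 10 degrees of freedom. The size of the anomaly, r, is an assumption: the Test-period peak divided by that participant's next highest sample.

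**Step 1: the protocol's own figure.** Log half-width = t(0.95; 10) × SD × √(χ²(0.80; 10)/10) × √(2/12) = 1.812 × 0.119 × 1.159 × 0.408 = 0.102. At a ratio of 100% this gives 90.30% to 110.75%, as tabulated. With SD 0.098 the AUC half-width is 0.084, giving 91.94% to 108.77%, also as tabulated.

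**Step 2: shift in the ratio.** In the balanced crossover each participant's log Test-minus-Reference difference has weight 1/12, so the shift is log(r)/12. The typical interval is exp(shift ± mean half-width), with the mean half-width taken from 400,000 simulated trials with a true ratio of 1.

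| r | Shift (log) | Ratio if kept | Shift / 0.102 | Mean half-width if kept | Typical 90% interval if kept |
|---|---|---|---|---|---|
| 1.3 | 0.0219 | 1.022 | 21% | 0.094 | 0.930 to 1.123 |
| 1.5 | 0.0338 | 1.034 | 33% | 0.105 | 0.931 to 1.149 |
| 2.0 | 0.0578 | 1.059 | 57% | 0.135 | 0.926 to 1.212 |

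If the value is removed, the ratio is 1.000 and the typical interval 0.918 to 1.090 (mean half-width 0.086). The 1.000 holds by construction, because the next highest sample is taken to be the true Cmax.

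**Step 3: would SAP 6.1 have caught the value?** The affected participant has the largest of the 12 residuals in 32%, 59% and 94% of trials for r = 1.3, 1.5 and 2.0. One residual is always the largest, however, and any given participant has it 8% of the time (1/12) with no anomaly. SAP 6.1 relies on visual judgement, so any cut-off is an assumption. In 200,000 trials:

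| Cut-off assumed | r = 1.3 | r = 1.5 | r = 2.0 |
|---|---|---|---|
| Internally studentized residual above 2 | 20% | 44% | 88% |
| Bonferroni 5% limit, externally studentized | 4% | 13% | 52% |

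For the smallest anomaly the two routes seldom differ, because 6.1 would usually not have picked the value up. It is also doubtful that a peak 1.3 times its neighbour counts as grossly inconsistent.

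**Step 4: AUC.** This used one-compartment profiles at the protocol's sampling times, with assumed half-lives of 30 and 60 h and absorption rates of 0.6 and 1.2 per h. One value at 24 or 48 h that is 1.5 times too high moves the AUC ratio by 0.7 to 0.9% (kept against removed). At 2 times too high the shift is 1.3 to 1.6%. Up to 8 h the shifts are at most 0.24% and 0.45%.

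**Step 5: the wording points.**

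- *Missing in tables, possibly excluded from analysis.* An analyst who judges a value anomalous and blanks it in the tables would ordinarily not let it define Cmax. The text permits that outcome but does not lead to it.
- *BLQ between quantifiable values.* The zero rule covers data presentations, not parameter derivation, and the anomalous-value rule names this exact case. The specific rule governs on a natural reading. A zero used in a table would lower that time point's mean by 1 − 11/12 = 8.3%. A zero carried into AUClast at 24 or 48 h would move the AUC ratio by 1.6 to 2.3% on the Step 4 assumptions, but no passage says to do so.
- *Biased parameters.* An estimate known to be biased is left out. The vomiting sentence asks the pharmacokineticist to judge whether a given case is of that kind. The two sentences fit together.

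**The case for a change.** The strongest case for a change is that the SAP already asks for more in neighbouring places. A known biased parameter must be footnoted (5.3.1), and a departure from the planned model must be justified (6.1), but a dropped concentration has no visible equivalent. The dropped value has already passed the assay check, and the label may rest on comparison with other participants, which overlaps with what a model outlier is. Protocol 9.3 promises that the SAP will set out how spurious data are handled. In an open-label study with unblinded data reviews allowed (SAP 7), a decision not fixed before modelling could be made with the ratio in view.

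Part of this stands: the visible text has no rule on reasons or timing. Three things limit it.

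- The two rules act at different levels, one on concentrations and one on residuals, so nothing is contradicted. SAP 6.1 promises an investigation, not a reported result with and without the value, so a compulsory paired table would go beyond the standard it is meant to match.
- An excluded value does not disappear. Protocol section 9.3.2 on PK statistics lists the concentrations and plots individual profiles, and the set-to-missing rule is confined to summary tables and median plots. With complete data, a reader who sees a dropped Test peak can recover the Cmax ratio with it kept by multiplying by r^(1/12), though not the interval.
- Text directly after the vomiting paragraph in SAP 5.3.1 is blacked out, so the absence of such a rule is established only for what can be read.

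**Conclusion.** No change to the plan is needed. This is a gap that a competent PK analyst fills sensibly: the discretion covers only grossly inconsistent values whose assay result has been confirmed, and following it does not produce a wrong estimate. Keeping an erroneous peak would itself distort the ratio and widen the interval, as the table shows.

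If such a value occurs in Cmax at 1.5 to 2 times the next sample, the choice moves the ratio by 3.4 to 5.9%, or 33 to 57% of the planned half-width. That is noticeable at 12 participants. With no hypothesis or decision rule (SAP 5.1), it overturns no formal conclusion. AUC effects are about 1.6% or less on the assumed profiles.

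These sizes rest on the assumed anomaly and half-lives and on the planning SD of 0.119. The documents give no rate at which such values arise. Listing any excluded concentration with its reason, decided before the model is run, is good reporting practice that the study team can follow under the SAP as written.
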